### 3.3 Ethnographic case study fieldwork and analysis incorporating realist evaluation

Organisational ethnographers will use longitudinal observations, interviews and documentary analysis to assess what happens in each site and record service changes made, with input from the frontline teams.

The case studies will be formative and exploratory; this means that findings will be fed back to the teams on an ongoing basis to help them develop and adapt their approach, and reflect on what has worked well or less well

Understanding how frontline staff use patient experience data for service improvement - an exploratory case study evaluation.

Protocol V1 09.02.16 HRA 180418

and why. A 'focused ethnography' approach will underpin the case studies. Focused ethnographies share many characteristics with classic ethnographies i.e. they are exploratory rather than hypothesis-testing; elicit unstructured data in the form of field notes and transcripts; involve a small sample, collect rich data and result in narrative description. Unlike classic ethnography, rather than embedding a sole researcher in a setting for a lengthy continuous period, more targeted observation periods are used.

There will be two main formal interviewing periods at the start and end of the quality improvement work, with a smaller number of interviews with key team leads at the midway point. The exact number of interviews to be conducted will depend to some extent on the composition of the frontline teams (including patients and family members) from each site, but we estimate a maximum of 10 at the beginning and end of the intervention, with 2-3 key improvement leaders on each ward at the mid-point, and 2-3 senior managers at the end of the fieldwork period, totalling approximately 25 in each site. In addition they will observe all the learning community meetings and webinars, and conduct observations for approximately 10 days in each site. The observation periods will include opportunities to record further informal conversations with members of the teams, as well as observing quality improvement meetings and workshops, general staff meetings, and reviewing meeting notes and improvement plans. Formal interviews will be recorded and transcribed verbatim; detailed observational fieldwork notes will be written by the ethnographers. Ward team members will be invited to keep a diary of their experiences and reflections and contribute this to the documentary analysis if they wish.

With the help of the frontline teams, the ethnographers will complete a 'service improvement log', recording planned and implemented changes as a result of the project, and categorising them as small-scale change; process redesign within team; process redesign between services; and process redesign between organisations (the categorisation used previously in HS&DR study 10/1009/14 on accelerated experience-based co-design).

The separation of patient experience evidence from the process of collecting and analysing it at local level is somewhat artificial, as collecting such data can itself be part of building momentum for their use in improvement and generating momentum for cultural change. Frontline teams involved in this study will be invited to engage in local data collection as well as using existing sources such as survey data or patient comments; comparisons between cases looking at how this is approached and what influence it has will form part of our ethnographic observations. However, our focus is primarily on the stage of using rather than collecting experience evidence.

Our analysis of the case studies will draw on realist evaluation methods (25). The aim is to 'make sense' of different patterns of actions and outcomes, understanding why, for whom and in what circumstances particular approaches work or not, rather than developing a predictive model. Realist evaluation produces generalisable findings, but does so by disaggregating interventions into component middle-range theories which we can then reasonably apply in other settings. In practice Trusts are likely to use a mix of complementary data sources and approaches; the toolkit will therefore include advice on how these may be used effectively in different circumstances and for different audiences.

When introducing change in complex systems, there are ideally two 'evaluations'. One is an internally-facing evaluation, usually done by the staff in the organisation, that asks 'how is this project going here?' This typically uses techniques like plan-do-study-act, and the data sources are chosen accordingly. Another kind of evaluation, which may draw on some of the same data, analysed differently and supplemented by other data, asks 'what general conclusions can we draw about the interaction between context, mechanism and outcome?' We will encourage and support staff in the first task and draw on realist methods to achieve the second, using

Understanding how frontline staff use patient experience data for service improvement - an exploratory case study evaluation.

Protocol V1 09.02.16 HRA 180418

both the results of the teams' own evaluation and the service improvement logs, and the ethnographic material collected. The analytic process will be supported by NVivo coding software. Coding will be both deductive and inductive, with codes derived both from organisational change theory and existing empirical literature, and from emergent themes in the data collected, focusing on the context-mechanism-outcome formula.

This study will run in parallel with the RAMESES II study to develop methodological standards for realist evaluation (HS&DR 14/19/19). The principal investigator on RAMESES II, co-applicant [name], and lead researcher [name], are both based at the University of Oxford. [name] will provide methodological and analytic support to this work as part of his (already funded) RAMESES II study.

Whilst realist evaluation will inform and guide elements of the analysis, we recognise that clearly articulating mechanisms of change and distinguishing these from aspects of context can be challenging (26). We will also adopt a wider comparative case study analytic approach as outlined by Fitzgerald and [name], taking an interpretive and holistic approach to understanding each case and how it compares with others (27-30). Comparative case study analysis lends itself to 'the exploration of complex "how" and "why" questions' (29:481) and will provide a rich source of information, understanding and pattern detection to inform a toolkit for the NHS. As in any case study design, gathering contextual information about concurrent events such as CQC inspections and changes of leadership will be an important component of data collection. Participants will be invited by the ethnographers to reflect on the significance of such contextual factors.

The face-to-face learning community meetings with frontline teams are very much intended to be two-way discussions rather than simply passive dissemination of research findings. The frontline teams and the patient advisers will contribute formatively to the analysis as well as using it to help them plan their next steps. Their feedback on the issues identified by the ethnographers and their response to the interpretations of the research team will be an important contribution to our understanding of the context and mechanisms at play in each site.

Given the fluid and evolving nature of the interventions we anticipate, we do not propose to conduct a formal cost analysis in each site for this study, though we will ask teams to work with the ethnographers to keep a record of numbers of meetings held and numbers of staff and patients/family members attending, to compare the level of effort and intensity involved with the number and type of changes made in each case. Our priority will be to focus on the process of using experience data of different types and the impact in terms of service improvements and changes in measured patient experience.

### 3.4 Post-intervention survey

The local baseline patient survey will be repeated a year on with a new set of patients to measure what, if any, change has occurred in measured patient experience following local quality improvement work. This will again be a postal survey with the same anticipated sample size of 240 per ward and will be sent to a census of all discharged patients from the six participating wards.

Results will be compared to data from the pre-intervention survey to see if there are any detectable ward-level changes to question scores. To explore whether ward level changes are observable at a Trust level, results (for those questions that map) will also be compared to Trust level data from the most recent NHS Adult Inpatient Survey.

The main outcome measure (or measures if all wards cannot be evaluated on the same measure) used for evaluating change will be determined through discussions amongst the research team, the project steering

Understanding how frontline staff use patient experience data for service improvement - an exploratory case study evaluation.

Protocol V1 09.02.16 HRA 180418

group, and with input from each ward team. This approach has the added benefit of allowing participating Trusts to be involved in the selection of measures, increasing their sense of ownership and 'buy-in' to the study.

Forty-eight in-depth interviews with patients and family or carers will also be carried out to gather more detailed information on the quality of the experience of recently discharged patients.

Reports showing survey and interview data for each case study site will be generated. They will detail:

- Response rate information
- The demographic profile of respondents
- Results for each question in the survey (with historical and Trust-level comparisons where appropriate). Caveats about interpretation of the data and the limits of significance testing will also be noted.
- Free text comments included as part of the survey
- Results from the in-depth interviews

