Whilst the NHS Inpatient Survey shows small incremental improvements in some aspects of experience, including information provision, communication with staff, hospital cleanliness, and privacy (12), the pace of change remains slow on some of the most important questions for person-centred care (12-13). Only 54% of patients feel 'definitely' as involved as they want to be in decisions about their care, and only 50% feel doctors and nurses 'definitely' gave their families all the information they needed (12). Furthermore, 79% of patients said they had not been asked during their stay in hospital to comment on the quality of their care. Although this was an improvement on the 86% saying they had not been asked in 2012, it nonetheless indicates a substantial missed opportunity to learn from patients.

[name] Board research into how Trust boards use patient experience data found substantial variation in what data were collected but more importantly in the degree to which they were effectively analysed and used to improve services (14). Strikingly, the research found that over 95% of the time, hospital boards' minuted response to patient experience reports was to note the report but take no further action. Examples where patient experience data was used to spark debate and action were rare, as were examples of non-executive directors challenging performance on patient experience measures. Understanding how to use qualitative evidence, including narrative and observational data, as well as numerical evidence can be

Understanding how frontline staff use patient experience data for service improvement - an exploratory case study evaluation.

Protocol V1 09.02.16 HRA 180418

challenging (14-16), and this is undoubtedly one of the key areas where Trusts need support and training. Meanwhile, they also face an explosion of online sources of patient experience data and social media (e.g. NHS Choices, Care Connect, Patient Opinion and Twitter) with little guidance on how to use them.

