#### 3.2. Establishing and supporting a learning community and developing frontline interventions

The six frontline teams will join a facilitated learning community to share and discuss findings from the baseline data. The initial meeting will be a two-day event in Oxford. Learning sessions will include presentations on different approaches to learning from and improving patients' experience; different features, uses, strengths and limitations of both quantitative and qualitative data; how to include experiences of 'seldom heard' groups; the evidence base for various quality improvement approaches. Teams will be offered improvement science support through NHS England.

Teams will then develop and implement their own interventions and measures and select priorities for improvement. Although we will not want to constrain ward teams' choice of focus, we will encourage them to consider, for example, the experience of frail elderly people and/or people with dementia. Given the topical importance of this we anticipate it might well be an attractive choice for one or more wards. This would allow for interesting experimentation with collecting and using carer/visitor experience data, and using techniques such as staff- or user-led observation, shadowing and 'in your shoes' exercises. Regardless of whether any of the sites choose to focus specifically on the experiences of a particular 'seldom-heard group', we see this as an important

Understanding how frontline staff use patient experience data for service improvement - an exploratory case study evaluation.

Protocol V1 09.02.16 HRA 180418

issue for all of the participating wards. If services are to provide a good experience to all of their users, they must be mindful of issues of diversity and ensure that care and information are tailored, where possible, to meet the needs of different patients and groups. To that end, we envisage encouraging staff to give consideration to issues related to diversity when planning interventions, and to identify areas where these may need adaptation or tailoring to be of greatest benefit to different groups.

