### 3.5 Synthesising analysis, writing up and preparation of toolkit

Following the completion of the fieldwork, the qualitative and quantitative data from Phase 2 will be brought together by the whole research team to create an overarching understanding of what changes were made and how in each site; what facilitated or hindered the process; how different types of data were received and acted on; what impact (if any) the process had on measured patient experiences; and what we can learn about successful strategies and pitfalls to include in guidance for the NHS. Early explanations will be tested and refined at the final learning community meeting with staff and patient and family advisers. We have scheduled a writing workshop for the research team in month 22 and again in month 25; this is an approach we have used successfully in the past to share out writing tasks and produce and share initial drafts, which will then be refined further in between workshops. From these workshops we will produce both the final NIHR report and the NHS toolkit (see dissemination). We have allowed six months for this process; although analysis will have been ongoing since the start of fieldwork, it is our experience that successful analysis requires repeated revisiting and reflection on the data to develop a nuanced account.

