## 7.2 Assessment and management of risk

This research involves minimal risk to participants. Ethnographic observation in NHS settings raises some potential ethical challenges if patient care is being observed. However, in this case the focus of the observation is on the quality improvement process, and will not include any direct observation of ward care or patients who are currently being cared for. The observations will thus be mainly of meetings and workshops, supplemented by interviews with participants in the frontline ward quality improvement teams (including user and carer team members) and documentary analysis. We have drawn on advice from our lay co-applicant who is a lead reviewer for an NHS ethics committee, an ethics consultant to the Research Design Service and research ethics trainer.

Staff involved in local improvement interventions may conduct their own patient interviews or observations, but these will not form part of the research and will be treated as service improvement work.

In order to measure changes in patient experience as a result of the quality improvement work, we will conduct a baseline survey and interviews with recently discharged medical ward patients, and repeat this after the intervention with another group of recently discharged patients. Patients taking part in the baseline and follow-up survey or interviews may feel some emotional distress as they recall details of their illness or their hospital care experiences. It will be made clear to survey respondents that their participation is voluntary and they can choose to withdraw or not return the survey. If a patient or family member becomes distressed during an interview, the researcher will immediately ask if they would like to pause or stop the interview. The researcher will be trained in how to deal with this situation. Patient information leaflets will stress that further participation in the interviews is voluntary and that consent may be withdrawn at any time without adverse consequences.

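### The ward-level survey comparison is an uncontrolled before-after contrast, yet its result is to be read as the project's impact; planned data could show background change beside it

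*Protocol*

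**What the plan says.** Section 3.4 of the protocol fixes the main numerical comparison: "Results will be compared to data from the pre-intervention survey to see if there are any detectable ward-level changes to question scores". The two waves hold different people: "The local baseline patient survey will be repeated a year on with a new set of patients".

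The same section adds a second comparison. For questions that map, results "will also be compared to Trust level data from the most recent NHS Adult Inpatient Survey". Its stated purpose is "To explore whether ward level changes are observable at a Trust level". Objective d in section 2 repeats this comparison.

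Two places give the survey change a causal meaning. Section 7.2 explains the surveys with the words "In order to measure changes in patient experience as a result of the quality improvement work". Section 3.5 lists among the questions for the synthesis "what impact (if any) the process had on measured patient experiences", which feeds the final report and the toolkit.

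Section 3.2 says of the wards: "Teams will then develop and implement their own interventions and measures and select priorities for improvement". All six wards are surveyed in both rounds and all six join one learning community. Section 3.3 plans a service improvement log of planned and implemented changes. Its cross-case comparison is interpretive, and no contrast of survey change between wards is described.

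**The concern.** A ward's change over a year mixes three things: the project's effect, whatever would have happened anyway, and a different set of responding patients. The comparison in 3.4 cannot separate them. A larger sample would not help, because it would make drift significant more often.

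The protocol itself shows that scores move without this project. Section 1 describes small incremental gains on some Inpatient Survey items. It also gives one larger movement, in the share of patients not asked to comment on their care: "Although this was an improvement on the 86% saying they had not been asked in 2012", the later figure being 79%.

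Upward drift would make the project look successful in wards where it did nothing, and downward drift would hide a real gain. Either could reach the toolkit as a finding about which strategies work.

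**Working it through.** **Inputs.** From section 5.2: 240 patients per ward per wave, 50% response, a stated minimum detectable difference of 11 percentage points. From section 1: 86% and 79%. Assumed, because not stated: a two-sided 5% test and, where power is used, 80%.

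**The plan's own figures.** 240 × 0.50 = 120 responses and 240 × 6 × 2 = 2880 surveys, as stated. The 11 points cannot be confirmed without the error rate, power and baseline proportion. At two-sided 5% and 80% power, 120 per wave detects a rise of 17.7 points from 50%, 13.9 from 75%, 12.4 from 80% and 10.6 from 85%, so 11 corresponds to a baseline near 84%. It also equals 1.96 × SE at 75% (10.96), which has no power term. I use 11 only as a yardstick.

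**Drift as large as the quoted item, no project effect.**
- Drift = 86 − 79 = 7 points; 7/11 = 64% of the yardstick.
- SE = √(0.86 × 0.14/120 + 0.79 × 0.21/120) = 0.0488, or 4.9 points.
- z = 0.07/0.0488 = 1.43.
- P(significant improvement) = P(Z > 1.96 − 1.43) = 0.30, against 0.025 with no drift. The pooled-variance version gives 29.6%.
- If all six wards were tested on such an item: 1 − (1 − 0.296)^6 = 88% chance of at least one significant improvement, against 1 − 0.975^6 = 14% with no drift.

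**Smaller drift.** Take SE = √(2p(1 − p)/120), which is 6.45 points at p = 0.50 and 5.59 at p = 0.75. The chance of significance in either direction is 1 − Φ(1.96 − d/SE) + Φ(−1.96 − d/SE):

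| Assumed drift d | p = 0.50 | p = 0.75 |
|---|---|---|
| 0 points | 5.0% | 5.0% |
| 2 points | 6.1% | 6.5% |
| 3 points | 7.5% | 8.4% |
| 5 points | 12.1% | 14.5% |

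**Does the Trust-level comparison remove drift?** Not as written. Removing drift needs the Trust's change over the same interval. One wave gives a level, and only for mapped questions.

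**Precision of a between-ward contrast.** Subtract the mean change in k wards not targeting the question. With equal response numbers, the SE is multiplied by √(1 + 1/k):
- k = 5: 1.095, so 11 points becomes about 12.0.
- k = 3: 1.155, so 12.7.
- k = 2: 1.225, so 13.5.
- k = 1: 1.414, so 15.6.

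These count sampling error only. If true ward changes varied with an SD of 4 points (assumed), then at p = 0.50 and k = 5 the SE is √(6.45² + 4²) × 1.095 = 8.3 points. That is about 29% above 6.45.

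**Bias of that contrast.** If the other wards gain a share s of an 11-point effect, the contrast expects 11 × (1 − s): 5.5 points at s = 0.5, and 0 at s = 1.

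**The case against.** The strongest reply is that the other five wards are not controls. All receive the intervention over the same period and share meetings, a virtual campus and webinars. Subtracting their change removes any benefit the process brings to all wards, which is part of what 3.5 asks about. Section 3.4 would also accept one main measure for all wards, and 3.2 encourages every ward to consider the same patient groups. On a question that all wards target, no contrast exists. Non-targeted questions are an imperfect reference too, since better engagement could lift scores generally. Finally, three high-performing and three mixed Trusts need not drift alike. All of this stands. A reader might infer that attribution should rest on the between-ward contrast alone; the documents do not support that.

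A reader might also infer that wards are compared only with their own past. They are not, because 3.4 plans the Trust-level comparison as well. Nor is the 30% a forecast. It rests on one item, not shown to be in the questionnaire, in a section that otherwise describes small changes and slow progress on some of the most important questions.

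The protocol is modest in other ways. Section 3.4 elsewhere speaks neutrally of change after the work, and the survey is one part of the evidence. Reports carry caveats on interpretation and significance testing, and 3.3 collects concurrent events. The causal phrase in 7.2 sits in a risk section and is not an analysis rule. These points lower the stakes, but none of the caveats names background change over time.

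Estimator details may be left to an analysis plan. The choice of comparison and its causal reading, however, are stated in the protocol.

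**Conclusion.** The point holds in a limited form. The ward-level test is an uncontrolled before-after comparison a year apart in different patients. Sections 3.5 and 7.2 give it a causal reading, and the Trust-level comparison is not built to remove drift.

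The size depends on drift in the study years, which is unknown. At 7 points, about 30% of wards with no project effect would show a significant improvement. At 5 points, 12% to 15% would be significant in either direction instead of 5%; at 2 points, 6% to 6.5%. All figures assume 120 responses per wave and a two-sided 5% test.

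The survey data already planned can give a rough view of background change. They cannot turn six concurrently treated wards into a controlled study. The between-ward contrast removes only drift common to the wards, and any common effect with it. It therefore belongs beside the raw change, not in its place.

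**What to change.** - **3.4, targets.** Before any follow-up response is opened, record from the service improvement log which survey questions each ward's changes were meant to move.
- **3.4, secondary analysis.** For each targeted question, report next to the raw change the ward's change minus the mean change in wards not targeting it. Also report the ward's change on its non-targeted questions.
- **3.4, Trust-level data.** Where questions map, show the Trust's Inpatient Survey change over the matching years, not only the latest level.
- **3.5 and 7.2, wording.** In 7.2, replace the causal phrase with 'following', the word 3.4 already uses, and align the impact question in 3.5. State that the raw change and the contrasts are interpreted together.

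**Cost.** Protocol wording, a short question-to-ward mapping, an earlier wave of Trust-level results and some extra analysis; no new ward survey. Intervals for the contrast are at least 10% wider with five comparison wards and 15% with three, and wider still with fewer wards or if wards' true changes vary. The contrast is biased toward zero because learning is shared, and it is unavailable for a question that all wards target.

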### 3.1 Baseline survey of medical patients' experiences

Case studies will begin with a baseline postal experience survey of medical patients discharged from each ward over three months. The questionnaire will focus on experience of four areas of care:

- Referral to service and accessing care, such as route of admission to the hospital and information received on or prior to admission
- Inpatient care, particularly focusing on relational aspects of care, including involvement in decisions and interactions with ward staff
- Discharge, such as information provision, discharge planning and danger signals to watch out for at home
- Support for self-management, such as support and information received for managing health day-to-day

A database of questions has been compiled mapped against the four areas of care. The questions are drawn from extensively tested, reputable sources such as the NHS Adult Inpatient Survey, Oxford Patient Involvement and Experience scale (OxPIE), previously developed questions about self-management and demographic indicators.

The survey will be administered using a postal methodology. Fieldwork will last for 12 weeks with two reminder mailings being sent to non-responders during this period. We propose to survey a census of all discharged patients from each of the six medical wards in a given three month period, with an anticipated sample size of 240 patients per ward. (See also 'sample and recruitment' below).

The pre-and post-intervention surveys should be viewed as part of the overall package of information collected rather than the only source of evidence. The survey will be used alongside the in-depth interviews (see below)

Understanding how frontline staff use patient experience data for service improvement - an exploratory case study evaluation.

Protocol V1 09.02.16 HRA 180418

and the ethnographic work to provide an understanding of the changes that have been made within different sites and to gauge the impact of these.

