#### Baseline and follow up survey of patient experience

Size of sample: 240 per ward at baseline, and a further 240 per ward at post-intervention follow-up. Total 2880 across six wards. Expected response rate of 50%.

Response rate data from the NHS Friends and Family Test suggests that on average in acute Trusts approximately 80 people are discharged per ward every month. Using this as a guide, we anticipate an estimated sample size of 240 patients per ward. The average sample of 240 patients per ward should provide 120 responses, assuming a 50% response rate (the response rate for the NHS Inpatient Survey 2013 which uses a similar methodology was 49%). This will allow for a minimum detectable difference of 11 percentage points for wards in the pre and post surveys; a good compromise between sample power and avoiding an excessively long sampling period. This minimum detectable difference of 11 percentage points is calculated based on the number of responses we believe to be achievable from the survey based on typical ward-level activity. Achieving a larger sample and a greater sample power would involve increasing the numbers of patients going through the medical wards in the three month sampling period, and this is out of the research team's control. As such, we will not have access to the kinds of sample sizes required for high precision estimates and detection of small changes. Due to this, the pre-and post-intervention surveys should be viewed as one part of the overall package of information collected rather than the only source of evidence.

Sampling technique: Census of every patient discharged from the ward over a 3-month period at baseline and again at follow-up.

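### Ward teams may help choose the main outcome after discussing their baseline scores, so the pre-post change on a low-scoring choice can rise through regression to the mean alone

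*Protocol*

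**What the plan says.** Section 3.4 gives a procedure for the main outcome and no outcome: "The main outcome measure (or measures if all wards cannot be evaluated on the same measure) used for evaluating change will be determined" through discussion among the research team and steering group, with each ward team contributing. The section gives no date for the decision and no rule for making it.

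The order of events comes from two other sections. Section 3.1: "Case studies will begin with a baseline postal experience survey of medical patients discharged from each ward over three months". Section 3.2: "The six frontline teams will join a facilitated learning community to share and discuss findings from the baseline data", followed later in that section by "Teams will then develop and implement their own interventions and measures and select priorities for improvement".

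The comparison is set in section 3.4: "Results will be compared to data from the pre-intervention survey to see if there are any detectable ward-level changes to question scores". The follow-up respondents are different people: "The local baseline patient survey will be repeated a year on with a new set of patients". There are no comparison wards. The one outside reference is Trust-level NHS Adult Inpatient Survey data, for questions that map, and its stated use is to see whether ward changes are visible at Trust level.

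On size, section 5.2 says: "The average sample of 240 patients per ward should provide 120 responses, assuming a 50% response rate". It gives a minimum detectable difference of 11 percentage points per ward.

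**The concern.** A team that has just discussed its own scores and is asked to set improvement priorities may well turn to the questions on which it did badly. If the main outcome follows those priorities, one baseline figure serves both as the reason for the choice and as the before-value. A question picked because it looked low is, on average, picked partly for an unlucky sample. Surveying new patients a year later does not help, because the error sits in the baseline score, and there is no control group to show the same drift.

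The result matters beyond the ward reports. Section 7.2 describes the surveys as the means of measuring change resulting from the improvement work. Section 3.3 counts change in measured experience among the study's priorities. Section 3.5 carries the impact on measured experience into the synthesis that informs the NHS toolkit. Among wards that choose this way the bias has the same direction, so comparing or pooling cases does not cancel it.

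**Working it through.** **The plan's own figures.** 80 discharges × 3 months = 240 per ward; 240 × 50% = 120 responses; 240 × 2 surveys × 6 wards = 2880. All agree with the protocol. The 11 points cannot be reproduced uniquely, because significance level, power and baseline proportion are not stated. One match is the two-sided 5% critical difference at 75%: 1.96 × √(2 × 0.75 × 0.25 / 120) = 10.96 points. The present point does not depend on that figure.

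**Inputs.** From the protocol: 120 responses at each survey, independent samples. Assumed, because the documents do not give them: 20 candidate questions, mean score 65%, true between-question SD τ of 4 to 15 points, correlation 0.3 between questions in sampling error, no true change, and the lowest baseline score chosen.

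**Expected spurious rise.** The sampling SE of one score is √(0.65 × 0.35 / 120) = 4.35 points, so SE² = 18.96. The part of the error shared by all questions does not affect which one is lowest and averages to zero. The remaining variance is v = (1 − 0.3) × 18.96 = 13.27. The expected minimum of 20 standard normal values is −1.867, so

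rise = 1.867 × v / √(τ² + v) = 24.78 / √(τ² + 13.27).

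| True SD τ (points) | √(τ² + 13.27) | Rise (points) | False improvement (simulated) |
|---|---|---|---|
| 4 | 5.41 | 4.6 | 10.0% |
| 8 | 8.79 | 2.8 | 6.4% |
| 10 | 10.64 | 2.3 | 5.3% |
| 12 | 12.54 | 2.0 | 5.0% |
| 15 | 15.44 | 1.6 | 4.6% |

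The last column is the share of simulated wards with a significant rise (two-sided 5% test, improvement side, nominal 2.5%). Simulated mean rises agree with the formula to within about 0.1 to 0.2 points; small differences come from whether each question's variance follows its own proportion.

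**Softer selection, same assumptions.**
- Random pick among the five lowest: +1.5 to +3.0 points and 4.1 to 5.9% for τ of 4 to 10; +1.1 to +1.3 points and 3.5 to 3.8% for τ of 12 to 15.
- Random pick from the lower half, τ of 12 to 15: +0.7 to +0.8 points and 3.1 to 3.4%.
- Choice unrelated to baseline score: 0.0 points and 2.5%.

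**Wider range.** With mean 70%, 5 to 40 questions, τ of 0 to 15 and correlation 0 to 0.3, choosing the lowest gives +1.0 to +9.0 points and 3.7 to 26%. The top end needs 40 uncorrelated questions with identical true scores, which is not realistic.

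**The case against.** The case on the other side is substantial.

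- **Timing is inferred.** Section 3.4 does not say when the main outcome is fixed. The measures that teams develop in section 3.2 may be local improvement measures, and section 3.3 separates the staff's own evaluation from the research evaluation. The research team and steering group also take part in the choice. This stands, so the point is what the plan allows and implies, not what it states.
- **No rule favours low scores.** The example focus in section 3.2, frail older people or people with dementia, is suggested for its topical importance, and teams may use other data. This also stands. A reader might infer that improvement is built in for every ward, but the text does not support that.
- **Two further scenarios are only possibilities.** A reader might infer that the outcome could be picked once follow-up data exist, or that a ward could pick a measure with no baseline value. Neither is planned. The first rests on silence about a date that an analysis plan may supply. Against the second, section 3.4 repeats the same survey and compares question scores.
- **Mitigation exists.** Results are reported for every question, with caveats on interpretation and significance testing, and the surveys are one part of a wider package. This guards against hidden questions and over-reliance. It does not correct a biased estimate on the measure designated as main, and the caveats do not mention regression to the mean.

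**Conclusion.** The concern holds in a conditional form. The protocol fixes who helps choose the main outcome but not when or by what rule, and its own sequence puts the baseline findings in front of the teams before measures and priorities are chosen. With the same baseline as comparator and no control wards, a choice that leans towards low scores can show improvement with no real change.

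For the lowest of 20 questions the artefact is about 1.6 to 4.6 points, or 15 to 42% of the 11-point detectable difference (1.6/11 and 4.6/11), with false improvement in 4 to 10% of such wards instead of 2.5%. These sizes rest on the assumed number, spread and correlation of questions and on the strictest selection rule. A realistic spread or softer rule puts the artefact at the low end or below.

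This is worth correcting before baseline results are released. It is not a fatal flaw, because the study is exploratory and no success rule depends on a significant survey result.

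**What to change.** Amend section 3.4 as follows.

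1. Either set the main outcome, or a selection rule blind to ward scores, before baseline results go to the teams; or, if wards choose after seeing baseline, limit the choice to questions in the baseline questionnaire and lodge it, dated, with the steering group before the first follow-up mailing.
2. For any measure chosen after sight of baseline, report the change with an allowance for regression to the mean, for example against a shrunken baseline estimate, beside the raw change and the results for all other questions. Name this bias in the caveats already promised.

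A single outcome imposed on all six wards is not required. Wards design different interventions, and a common measure could miss what one of them set out to change.

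The cost is a few sentences of protocol text, a dated record, slightly less freedom for the wards and a little more analysis. Ward involvement in the choice is kept.
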